Visit / Contact	Screening	V1	C1	V2 ¹	Monthly contacts until delivery ⁶	V3	V4	C2	Safety Visit - Event-driven	RSV-associated MA-RTI Visit - Event-driven ⁷	Notes
Timepoint	D (-28) – D 1	D1 (24 ^{0/7} - 36 ^{0/7} weeks of gestation)	D8	D31		Delivery	D43 Post-delivery	D181 Post-delivery			For monthly contacts: Section 8.4.2.1 Additional contacts and/or visits can be made between Visit-2 and the Delivery visit if deemed necessary.
Administer Intervention (study vaccine / placebo)		•									Sections 6.1 and 6.2
Record administered intervention number		•									
Observe for 30 minutes post-dose		0									
Distribute maternal participant card	0	0									Section 8.3.6
Record Labor / delivery information						•					
Record pregnancy / delivery outcomes (Day 1 post-study intervention to Day 42 post-delivery)		0	0		0	•	0				Section 8.3.3 . Must submit Expedited AE report for an adverse pregnancy outcome
Train maternal participant/LAR on use of eDiary device		0									Section 10.3.8
Distribute eDiary device to maternal participant / LAR.		0									
Review eDiary entries		0	0	0					0 ⁴	0 ⁴	Section 8.3.1
Return eDiary device				0							

CONFIDENTIAL

214725 (RSV MAT-012)
Protocol Amendment 1 Final

Visit / Contact	Screening	V1	C1	V2 ¹	Monthly contacts until delivery ⁶	V3	V4	C2	Safety Visit - Event-driven	RSV-associated MA-RTI Visit - Event-driven ⁷	Notes
Timepoint	D (-28) – D 1	D1 (24 ^{0/7} - 36 ^{0/7} weeks of gestation)	D8	D31		Delivery	D43 Post-delivery	D181 Post-delivery			For monthly contacts: Section 8.4.2.1 Additional contacts and/or visits can be made between Visit-2 and the Delivery visit if deemed necessary.
Concomitant medications / vaccinations		•	•	•	•	•	•	•	•	•	Sections 6.8.1 and 6.8.3
All solicited AEs (Day 1 post-study intervention to 7 days post-study intervention)		0	0						0		Sections 8.3.1, 10.3.4 and 10.3.8
All unsolicited AEs (Day 1 post-study intervention to 30 days post-study intervention)		•	•	•					•	•	Sections 8.3.1, 10.3.4 and 10.3.8
Record of worsening of pre-existing medical conditions and/or obstetric complications (Day 1 post-study intervention to 180 days post-delivery)		•	•	•	•	•	•	•	•	•	Section 8.2.1.2
Pregnancy-related AESIs (Day 1 post-study intervention to 42 days post-delivery)		•	•	•	•	•	•	•	•	•	Sections 8.3.1, 8.3.3, 8.3.4 and 10.3.5. Must submit an Expedited AE report.
Suspected, probable and confirmed cases of COVID-19 infection (depending on		•	•	•	•	•	•	•	•	•	Sections 8.4.7

CONFIDENTIAL

214725 (RSV MAT-012)

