Visit 4	Day 43 after delivery	Day 31 - Day 61 after delivery
Contact 2	Day 181 after delivery	Day 166 - Day 201 after delivery
Infant participants		
Visit 1-NB (Birth) ^{d, e}	Birth	-
Recommended safety contact	Day 8	Day 7 - Day 10
Visit 2-NB	Day 43 after birth	Day 31 – Day 61 after birth
Contact 1-NB	Day 91 after birth	Day 84 - Day 98 after birth
Visit 3-NB ^f	Day 121 after birth	Day 111 – Day 141 after birth
Visit 4-NB ^f	Day 181 after birth	Day 166 – Day 201 after birth
Contact 2-NB	Day 271 after birth	Day 257 – Day 287 after birth
Visit 5-NB	Day 366 after birth	Day 331 – Day 401 after birth

^a Whenever possible the Investigator should arrange study visits at study days.

^b The investigator should endeavor to have the participants come in for the visits within this window.

^c Visit 2 (Day 31) may be replaced by Visit 3 (Delivery) in case of premature delivery. If the delivery date occurs prior to Day 31 post-study intervention, there will be no Visit 2 (Day 31).

^d If no cord blood was collected, an infant blood sample must be collected within 72 hours after birth.

^e If consent is not obtained within the allowed interval, but the parent(s) /LAR(s) still wish the infant to participate, consent may be obtained at any time until the Day 43 post-delivery/birth visit.

^f Visit may coincide with infant participant's routine care visit.

^g **For participants in whom a cesarean section is performed, the sample may be collected as soon as the participant arrives at the clinic and the intravenous line is inserted to prepare them for the cesarean section.**

Note: In times of special circumstances, refer to Section 8 for study procedures.

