
Infant participants:
 
 To evaluate safety up to 42 days post-birth in infants born to maternal participants who received a single IM dose of study intervention (RSV maternal vaccine or placebo). 	
 Number and percentage of infant participants reporting: 
 Neonatal / infant AESIs * from birth up to 42 days post-birth. * These include small for gestational age, low birth weight including very low and extremely low birth weight (<2500 g, <1500g, <1000g), congenital anomalies (major external structural defects, internal structural defects, functional defects), neonatal death (in an extremely preterm birth [22≤GA<28 weeks], in a preterm live birth [28≤GA<37 weeks], or in a term live birth) and preterm birth.¹ SAEs, (S)AEs leading to study withdrawal and MAEs from birth up to 42 days post-birth.

 To evaluate safety up to 365 days post-birth (1 year of age) in infants born to maternal participants who received a single IM dose of study intervention (RSV maternal vaccine or placebo). 	
 Number and percentage of infant participants reporting: 
 SAEs, (S)AEs leading to study withdrawal and MAEs from birth up to 180 days post-birth. SAEs, (S)AEs leading to study withdrawal and MAEs from birth up to 365 days post-birth.

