
Safety assessment:
 
Maternal participants:
 
 To evaluate the safety of a single IM dose of study intervention (RSV maternal vaccine and placebo) administered to maternal participants, up to 180 days post-delivery. To evaluate the worsening of pre-existing medical conditions and/or obstetric complications up to 180 days post-delivery, in maternal participants who received a single IM dose of study intervention (RSV maternal vaccine or placebo). To evaluate the occurrence of RSV-associated MA-RTIs in maternal participants who received a single IM dose of study intervention (RSV maternal vaccine and placebo) up to 180 days post-delivery. 	
 Number and percentage of maternal participants reporting: 
 SAEs, (S)AEs leading to study withdrawal and MAEs from Day 1 up to 180 days post-delivery. Number and percentage of maternal participants reporting: 
 Worsening of pre-existing medical conditions and/or obstetric complications from Day 1 up to 180 days post-delivery. Number and percentage of maternal participants reporting: 
 RSV-associated MA-RTIs from Day 1 up to 180 days post-delivery.

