4.4. End of Study definition

A participant is considered to have completed the study if he/she returns for the last visit or is available for the last scheduled contact as described in the protocol. Refer to [Section 10.7.2](#) for the definition of EoS.

EoS: Last subject last visit (LSLV) of infant participants (Visit 5-NB, Day 366 post-birth)

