¹ Approximately monthly contacts pre- delivery also occur within the timeframes described above and are described in Section 1.2.

² i.e. consent obtained.

³ If subsequent pregnancy occurs during the study, follow-up may extend up to 8 weeks post-birth of the infant from that subsequent pregnancy.

⁴ Neonatal AEs of special interest identified after Visit 2-NB (e.g., congenital anomalies) will continue to be reported as such.

⁵ SAEs and/or AESIs experienced by an infant born to the exposed mother will be reported (if become known to the site staff), even if the re-consent for infant participants is not provided.

⁶ ***Due to the change in the study requirements, RTI surveillance of the maternal participants will no longer be performed.***

The investigator or designee will record and immediately report all SAEs (including RTIs associated with hospitalization of a maternal or infant participant and serious adverse pregnancy outcomes), as well as all pregnancy-related AESIs and neonatal AESIs to the sponsor or designee via the Adverse Events Form and the corresponding Expedited Adverse Event Form. Reporting should, under no circumstances, occur later than 24 hours after the investigator becomes aware of an SAE, as indicated in Section 10.3.10 and Table 18. The investigator will submit any updated SAE/AESI data to the sponsor within 24 hours of it being available.

A post-study SAE is defined as any event that occurs after the end of the study. Investigators are not obligated to actively seek SAEs from former study participants. However, if the investigator learns of any SAE, including a death, at any time after a participant has been discharged from the study, and he/she considers the event to be reasonably related to the study intervention, the investigator will promptly notify the study contact for reporting SAEs mentioned in the Table 19.

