2041#*	Device, excluded by the protocol, was administered by mother up to Delivery	All	Immunogenicity
2050.Vx+*	Intercurrent medical conditions which are exclusionary as per protocol - infant	Visit 2-NB/Day 43 post-birth Visit3-NB/Day 121 post-birth Visit4-NB/Day 181 post-birth	Immunogenicity
2060.Vx+*	Concomitant infection related to the vaccine which may influence immune response - infant	Visit 2-NB/Day 43 post-birth Visit3-NB/Day 121 post-birth Visit4-NB/Day 181 post-birth	Immunogenicity

CONFIDENTIAL

Code	Condition under which the code is used	Visit (timepoints) where the code is applicable	Applicable for analysis set/endpoint
2070.Vx+*	Concomitant infection not related to the vaccine but may influence immune response - infant	Visit 2-NB/Day 43 post-birth Visit3-NB/Day 121 post-birth Visit4-NB/Day 181 post-birth	Immunogenicity
2050#*	Maternal intercurrent medical conditions which are exclusionary as per protocol up to Delivery	All	Immunogenicity
2060#*	Maternal concomitant infection related to the vaccine which may influence immune response up to Delivery	All	Immunogenicity
2070#*	Maternal concomitant infection not related to the vaccine but may influence immune response up to Delivery	All	Immunogenicity
2090.Vx	
Participants did not comply with blood sample schedule – infant:
 
 • For infants without cord blood, check the interval from birth to Visit 1-NB birth BS = 0 – 72 hours; • For PPS at Day 43 post-birth, check the interval from birth to Day 43 BS = 30 – 60 days; • For PPS at Day 121 post-birth, check the interval from birth to Day 121 BS = 110 – 140 days; • For PPS at Day 181 post-birth, check the interval from birth to Day 181 BS = 165 - 200 days 	Visit 1-NB/Birth Visit 2-NB/Day 43 post-birth Visit3-NB/Day 121 post-birth Visit4-NB/Day 181 post-birth	Immunogenicity

CONFIDENTIAL

Code	Condition under which the code is used	Visit (timepoints) where the code is applicable	Applicable for analysis set/endpoint
2100.Vx	Serological results not available	Visit 1-NB/Birth Visit 2-NB/Day 43 post-birth Visit3-NB/Day 121 post-birth Visit4-NB/Day 181 post-birth	Immunogenicity
2120.Vx	Obvious incoherence or abnormality or error in data	Visit 1-NB/Birth Visit 2-NB/Day 43 post-birth Visit3-NB/Day 121 post-birth Visit4-NB/Day 181 post-birth	Immunogenicity

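### The concluding maternal contact and infant visit may fall before the 180-day and 365-day safety windows they close, with no closing contact required afterwards

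*Protocol*

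**What the plan says.** **Endpoints.** Protocol Section 3 (Table 4) lists as a primary infant endpoint "SAEs, (S)AEs leading to study withdrawal and MAEs from birth up to 365 days post-birth". The corresponding maternal endpoint, which is secondary, is "SAEs, (S)AEs leading to study withdrawal and MAEs from Day 1 up to 180 days post-delivery". Infant RSV-associated LRTI and RSV-associated hospitalization are secondary endpoints over the same 365 days.

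**Windows.** Table 3 in Section 1.3 sets Visit 5-NB (nominal Day 366) at "Day 331 – Day 401 after birth" and Contact 2 (nominal Day 181) at "Day 166 - Day 201 after delivery". Footnote a asks for the nominal day where possible.

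**Conclusion of follow-up.** Tables 1 and 2 place study conclusion at Contact 2 and Visit 5-NB. Section 4.4 states: "A participant is considered to have completed the study if he/she returns for the last visit", or is available for the last scheduled contact. It sets no minimum elapsed time. Section 7.2 treats as withdrawn, for analysis, only those who miss the concluding visit or contact. On post-study events, Section 8.3.1 says: "Investigators are not obligated to actively seek SAEs from former study participants".

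**Infant surveillance.** Table 2 has a column of RTI surveillance contacts running from birth to Day 366, with SAEs and MAEs marked there for eCRF entry. Section 8.4.2.2 ends surveillance at 366 days after birth and names Visit 5-NB in parentheses as that endpoint.

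**Analysis.** SAP Sections 4.2.1.1 and 4.3.1.1 tabulate numbers and percentages on the Exposed Sets. The SAP's missing-data rules (Section 6.2.3) contain nothing for follow-up shorter than the stated window.

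**The concern.** A visit that closes an observation window should not come before the window ends unless something else covers the remainder. Here an infant seen at Day 331, or a mother contacted at Day 166, is within the protocol. No deviation is raised, the study-conclusion page can be completed, and the participant is analysed as having full follow-up. An event in the remaining days that nobody asks about is counted as no event, so the proportion can only move down.

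This matters more after Amendment 1. The amendment's purpose is continued safety follow-up of women already vaccinated and their infants. It promoted the 365-day infant SAE/MAE endpoint to primary and moved the primary completion date to Visit 5-NB. After discharge, Section 8.3.1 provides only for SAEs that the investigator happens to learn of and considers reasonably related. It gives no route for a new non-serious MAE, which also counts towards the endpoint.

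**Working it through.** **Day convention.** The documents give no figure for unobserved days, so the first step is to fix how a Day number converts to elapsed days. Comparing Table 3 with the sampling intervals in SAP Tables 7 and 8:

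- Day 21–46 becomes 20–45 days
- Day 31–61 becomes 30–60 days
- Day 111–141 becomes 110–140 days
- Day 166–201 becomes 165–200 days ("check the interval from birth to Day 181 BS = 165 - 200 days")

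All four fit elapsed days = Day number − 1.

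**Largest gap per participant.** Gap = window length − (earliest allowed Day − 1).

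- Infants: 365 − (331 − 1) = 35 days; 35/365 = 9.6%.
- Mothers: 180 − (166 − 1) = 15 days; 15/180 = 8.3% of the post-delivery days.

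If Day n were read as n elapsed days, the gaps would be 34 and 14. The SAP intervals support 35 and 15.

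**Mothers, full window.** The maternal endpoint starts at dosing. Assuming delivery at 40 weeks (my assumption) and dosing at 24 to 36 weeks, dosing to delivery is 112 to 28 days. The full window is then 292 to 208 days, and 15 days is 15/292 = 5.1% to 15/208 = 7.2%.

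**Effect on a reported percentage.** Assume a constant hazard and, as the worst case, everyone concluded at the earliest day with no later ascertainment. With true risk p, window L and gap g, the observed risk is 1 − (1 − p)^((L − g)/L).

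| Window | True risk | Observed, worst case |
|---|---|---|
| Infant, 365 days | 10% | 9.1% |
| Infant, 365 days | 50% | 46.6% |
| Maternal, 180 post-delivery days | 10% | 9.2% |
| Maternal, 180 post-delivery days | 50% | 47.0% |

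If only a fraction f is concluded at the earliest day, the shortfall is f times that difference. For a true infant risk of 10%, the observed figure lies between 10% (f = 0) and 9.1% (f = 1). The documents do not give f.

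**Does anything cover the gap?**

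- Mothers: no. The monthly contacts in Table 1 end at delivery, Amendment 1 stopped maternal RTI surveillance, and no maternal contact is scheduled after Contact 2.
- Infants: it depends on the reading. If the Table 2 surveillance contacts continue to Day 366 whatever the date of Visit 5-NB, the gap shrinks or closes. If Section 8.4.2.2 means that surveillance stops at Visit 5-NB, where Table 2 also places study conclusion, the maximum of 35 days stands. No passage says which.

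**After the fix.** With a last safety contact no earlier than Day 366 or Day 181, the gaps are 365 − 365 = 0 and 180 − 180 = 0.

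**The case against.** The strongest reply is that the intended period is clear and the effect small. Table 17 fixes collection at 365 days post-birth and 180 days post-delivery, not at the last visit. Table 3 steers visits to the nominal day. The windows are identical in both arms, everything is descriptive, and the signals that stopped enrolment (preterm birth and neonatal death) arise at or soon after birth, far from Days 331–365. The infant 180-day endpoint is covered by later visits. All of that stands and limits the point to modest under-ascertainment. It does not remove it: a stated collection period needs a contact to deliver it, and for mothers none is scheduled. Because the study is now fully unblinded, equal visit timing by arm should be shown, not assumed.

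A reader might go further in three ways that the documents do not support.

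- **That 35 infant days are certainly lost.** Table 2 marks SAEs and MAEs at surveillance contacts labelled to Day 366. The loss is conditional on those contacts stopping at Visit 5-NB.
- **That most of the 30-day unsolicited-AE window is unasked when Visit 2 does not take place.** The Table 1 row "All unsolicited AEs (Day 1 post-study intervention to 30 days post-study intervention" is not marked at the monthly contacts or Visit 3. Counting from Contact 1 (Day 8–12) would then suggest 30 − 12 = 18 to 30 − 8 = 22 unasked days. But the same row cites Section 10.3.4, which has events that are not medically attended collected at the following visit or contact. Footnote c to Table 3 also lets Visit 3 stand in for Visit 2 in a premature delivery.
- **That this biases the preterm-birth comparison between arms.** SAEs, MAEs and pregnancy-related AESIs are marked at the monthly contacts and Visit 3, and preterm birth and neonatal death are captured as AESIs. The missing mark touches only non-serious, non-medically-attended, non-AESI events.

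**Conclusion.** The point holds in a limited form. For mothers, the protocol permits conclusion up to 15 days before the 180-day window ends, and nothing is scheduled afterwards. For infants, it permits Visit 5-NB up to 35 days before the 365-day window ends. Whether those days are unobserved depends on passages that conflict and must be reconciled.

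The 180-day maternal and 365-day infant proportions can therefore be somewhat low. The worst-case illustration is 9.1% observed for a true infant risk of 10%. It assumes a constant hazard, everyone seen on the earliest day and no later ascertainment, so the actual effect is likely to be smaller. There is no evidence of a difference between arms. The point is worth acting on because one affected endpoint is primary and the remedy costs little.

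**What to change.** 1. **Closing contact.** Before the study-conclusion page is completed, require a telephone safety contact on or after Day 181 post-delivery (mothers) or Day 366 post-birth (infants) for anyone whose concluding contact or visit was earlier. Alternatively, make those days the lower limits of the two windows in Table 3 and keep the upper limits (Day 201 and Day 401).
2. **Infant surveillance.** State in Section 8.4.2.2 that surveillance contacts continue to Day 366 regardless of the Visit 5-NB date, so that it agrees with Table 2. This does not replace item 1: active contacts are only monthly outside the RSV season in seasonal regions, so the last one may still fall before Day 366.
3. **SAP.** Report by arm the number of mothers concluded before Day 181 and of infants concluded before Day 366.
4. **Minor, Table 1.** Mark unsolicited AEs at Visit 3 and at the first monthly contact after a Visit 2 held before Day 30, to match Section 10.3.4 and footnote c. Visit 2 is allowed from Day 21, so Days 22–30 may otherwise rest on Section 10.3.4 alone.

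The cost is one call for participants seen early, by contact methods the protocol already allows, plus one SAP count and the Table 1 marks. No new procedure or participant is needed.

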2. INTRODUCTION

2.1. Study rationale

GSK is developing an investigational respiratory syncytial virus (RSV) vaccine for administration to pregnant women in their late second and third trimester of pregnancy, with the aim of preventing RSV-associated lower respiratory tract illnesses (LRTIs) in their infants by transfer of maternal antibodies.

The investigational vaccine is an engineered version of the RSV fusion (F) surface glycoprotein, stabilized in the pre-fusion conformation. The F protein has been selected because it is a major surface antigen of the RSV virus that is well conserved among RSV-A and RSV-B subgroups. The RSV F protein is the main target of the neutralizing antibody response to RSV, which is considered essential for protection against RSV-associated severe disease [Magro, 2012]. Vaccination of pregnant women with the RSV F protein is expected to protect the baby against RSV (subtypes A and B) LRTI from birth up to 6 months of age.

In the RSV maternal program RSV preF3 vaccine safety, reactogenicity and immunogenicity has been studied in healthy non-pregnant women, 18-45 yoa (study RSV MAT-001 [NCT 03674177] tested 30, 60 and 120 µg dose-levels, completed; study RSV MAT-011[NCT 04138056] tested 60 and 120 µg dose-levels in co-administration with dTpa vaccine, ongoing) and in healthy pregnant women 18-40 yoa (study RSV MAT-004 [NCT 04126213], tested 60 and 120 µg dose-levels, ongoing) and in infants born to vaccinated mothers.

The 120 µg dose has demonstrated robust immunogenicity with no safety concerns identified. It was, therefore, selected for evaluation in the Phase *III* studies: the RSV MAT-009 confirmatory efficacy trial is ongoing and the RSV MAT-012 trial is planned to assess the safety, reactogenicity and immunogenicity in the high risk obstetric population.

High risk pregnancies represent up to 33% in the overall population of pregnant women [Holness, 2018]; however, women with high risk pregnancies will not be part of the pivotal RSV MAT-009 study, which will enroll healthy pregnant women. In order to collect proper information in this population, RSV MAT-012 study will enroll pregnant adult participants with prevalent obstetric complications or conditions which increase the risk of adverse pregnancy and neonatal outcomes: gestational diabetes, gestational hypertension, pre-eclampsia, fetal growth restriction, history of preterm labor in the current pregnancy, HIV infection or uncomplicated twin gestation.[ACOG, 2019; EPI-RSV-015, 2019; Kachikis, 2017]. This study will also enroll healthy pregnant adolescent participants, considered as a potential high risk group.

The objective of the RSV MAT-012 study is to evaluate the safety, reactogenicity, and immunogenicity of the single intramuscular 120 µg dose of the study RSV maternal vaccine compared to placebo, when administered in the second or third trimester of pregnancy in women with high risk pregnancies and in the infants born to the vaccinated mothers.

2.2. Background

Please refer to the current Investigator's Brochure (IB) for background information on RSV infection, the rationale for the maternal immunization approach described in this protocol, and information regarding pre-clinical and clinical studies of the RSV Maternal (RSVPreF3) vaccine and epidemiology studies of RSV infection.

2.3. Benefit/Risk assessment (Amended 15 March 2022)

The Sponsor has included provisions in this trial to ensure participant's safety. Safety monitoring has been and will be conducted throughout this study by an unblinded Independent Data Monitoring Committee (IDMC) and by the Sponsor. The study includes the establishment of a surveillance system which may facilitate detection of respiratory tract infections, in particular lower respiratory tract infections (LRTIs) in infants enrolled in the study. Measures to suspend the study should a potential safety issue be identified are described in Section 8.2.3.

Following a recommendation from the IDMC, the Sponsor made the decision to pause the enrollment, randomization and vaccination of participants in our active pregnant women studies, including RSV MAT-012, based on an observation of imbalance of the proportion of preterm births between the vaccine group and the placebo group in the RSV MAT-009 study. This pause was to allow for an evaluation of the available data in RSV MAT-009 to better understand the safety signal observed. Following a review of additional unblinded data from this trial in which a higher proportion of neonatal deaths reported in the treatment group compared to the placebo group was also observed, the Sponsor decided to STOP enrollment and vaccination in these studies.

The safety signals are being investigated and, although at this time a cause has not been determined, the Sponsor stopped active enrollment and further vaccination of participants in the RSV MAT studies enrolling pregnant women on February 25, 2022 as a precautionary measure. The study remains ongoing for safety follow-up. Participants already vaccinated and their infants will continue to be monitored until the end of the study.

